1 INTRODUCTION

This document describes the statistical procedures that will be utilized for the CISA protocol Safety of Simultaneous Vaccination with Zoster Vaccine Recombinant (RZV) and Quadrivalent Adjuvanted Inactivated Influenza Vaccine (allIV4) that was approved on September 7, 2022. This statistical analysis plan (SAP) describes the methods of statistical analysis. The initial draft SAP (Version 0.1) was developed prior to any data being analyzed in order to avoid bias. Any subsequent changes that occur to the study protocol warranting changes to the analysis procedures will be documented in the SAP (both draft versions (0.X) and the final version (X.0). Table 1 below will be used for tracking of changes to the SAP. In this study of 400 adults age ≥ 65 years, participants aged 65 to 69 years will be randomized (1:1) to receive either simultaneous RZV and allIV4 or RZV and HD-IIV4 using a permuted block randomization scheme stratified by Lead and Contributing Site. A separate permuted block, stratified by site will be allocated for subjects who are age 70 years and older.

Table 1. Statistical Analysis Plan Versions

Version	Date of Approval	Major Changes from Prior Version
0.1	TBD	NA
0.2	TBD	Section 3.3 – Exploratory objective # 7: Specified sample collection dates Section 8.1. – Primary Objective: Corrected age range
0.3	TBD	Added Under Study Objective Outcomes (SO1, SO2, EO1, EO2, EO3, EO5, and EO6): This information will also be presented by age-group for the subset of subjects aged 65-69 versus those subjects aged 70 years or older. No formal statistical hypothesis testing (i.e., no p-values) will be performed, only the confidence boundary of the difference will be presented. Added minor edits Added EQ-5D & EQ VAS Post-vaccination score description
1.0	11/27/2022	Minor edits provided by the CDC
2.0	5/7/2024	Corrected minor typo in description of EO4 in Section 8.3 Corrected minor typo in description of SO1 in Section 3.2

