4.4 Randomization

Participants aged 65 to 69 years will be randomized (1:1) to receive either simultaneous RZV and allV4 or RZV and HD-IIV4 using a permuted block randomization scheme stratified by Lead (Duke University) and Contributing Site (Johns Hopkins University). A separate permuted block will be allocated for subjects who are age 70 years and older. The project statistician will generate permuted block randomization schemes, which will be uploaded to REDCap (see below). The randomization schedule will not be available to the study staff, so the next randomization allocation will not be known before randomization occurs. Following confirmation of study eligibility criteria during Visit 1, participant randomization will be through REDCap with treatment allocation recorded on the case report form (CRF).

In the event that REDCap is unavailable, manual randomization will occur through the use of envelopes. The project statistician will prepare 20 envelopes per participant age group per site (total of 40 per site) that will use the same randomization strategy as the primary scheme embedded in REDCap. When an unblinded team member is informed of the participant's age group, he/she will pull the next envelope in order. In order to capture the allocation per subject, a separate form in REDCap will be used by the unblinded personnel to add the assignment. A log will need to be kept at the site capturing these instances.

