5.2 Analytic Issues

There are two sites participating in the study and analysis of the primary objective will be stratified by site (Duke University and Johns Hopkins University) to account for this unit of randomization. All objectives will be stratified by site when applicable. The alpha will be set at a one-sided 0.025 level for noninferiority testing and at the alpha 0.05 level otherwise. There will be no adjustments to the alpha level for multiple comparisons. Should an interim safety analysis be required, the alpha level will be adjusted to assure the overall type I error is maintained at the one-sided alpha 0.025 level for the primary outcome of non-inferiority.

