Post-vaccination EQ-5D and EQ VAS index values will be calculated by the lowest/worst index value scores from baseline. The changes from baseline for the index values will be assessed within vaccine group using a linear regression model adjusting for site since these will follow a normal distribution. The VAS minimum clinically important difference is 8, so categorical comparisons (less than 8 points, within 8 points, greater than 8 points) will be made using a Mantel-Haenszel statistic in a stratified analysis by site. The Mann-Whitney U test (Wilcoxon rank-sum test) will be used to compare the difference scores from baseline between the two vaccine groups for the index values and VAS.

The statistical tests described above will also be performed by age-group (65-69 years and ≥ 70 years). This testing will be considered exploratory with an alpha level of 0.05 with no alpha adjustment.

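### The between-arm test of quality-of-life change ignores the randomization strata, against the SAP's own site rule; it stays valid but may lose some power if site or age predicts the change

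*SAP*

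**What the plan says.** SAP 8.3, Exploratory Objective 8, describes three analyses of EQ-5D and EQ VAS change:

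- A linear regression of index change, adjusted for site, but assessed within vaccine group.
- A comparison of VAS change in three categories around the 8-point minimum important difference, by a Mantel-Haenszel statistic stratified by site.
- The between-arm comparison of the change scores: "The Mann-Whitney U test (Wilcoxon rank-sum test) will be used to compare the difference scores from baseline between the two vaccine groups", for index and VAS. No site or age term is named.

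The tests are then repeated in each age group, and "This testing will be considered exploratory with an alpha level of 0.05 with no alpha adjustment". Protocol 7.1.4 names the same plain rank test and sets alpha at 0.05 two-sided.

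SAP 5.2 gives a general rule: "All objectives will be stratified by site when applicable". For the primary objective it explains that site stratification is there "to account for this unit of randomization". On the allocation itself, SAP 1 adds to the site-stratified scheme for ages 65 to 69: "A separate permuted block, stratified by site will be allocated for subjects who are age 70 years and older". That makes four cells, two sites by two age groups.

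**The concern.** The two neighbouring analyses carry site explicitly and the rank test does not. Because the index regression is run within vaccine group, the rank test is, as written, the only between-arm test of index change. It is also the only between-arm test of the VAS as a score. A site-stratified form of the same test exists, so the qualifier in SAP 5.2 does not obviously excuse the omission, and neither document says why it would.

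Permuted blocks within cells balance the arms in each cell, so differences between cells hardly enter the arm comparison. A test that ignores the cells still counts those differences as noise. Where they are real, it rejects too rarely under the null and misses some true differences.

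**Working it through.** **The plan's own figure.** No sample size, SD or effect is stated for this test. The only sizing is for the primary endpoint, and it reproduces: (1.960 + 0.842)² × 2 × 0.14 × 0.86 / 0.10² comes out just above 189, so 190 per arm and 380 in total; 380 / 0.95 = 400.

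**Inputs from the documents.** 400 participants and 1:1 allocation (SAP 4.3, 4.4); about 220 at Duke and 180 at Johns Hopkins (Protocol 4.3); four blocked cells (SAP 1, 4.4); two-sided alpha 0.05 (Protocol 7.1.4).

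**Assumptions, not in the documents.** An even age split (cells of 110, 110, 90, 90), the arm effect, the shift in change score between sites and between age groups, and the shape of the distribution.

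**Large-sample argument.** Let ρ be the share of change-score variance explained by the cells. With balanced cells the unstratified statistic is about √(1−ρ) times the fully stratified one. With m the mean of the stratified statistic:

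- size of the plain test = 2Φ(−1.96/√(1−ρ))
- its power = Φ(m − 1.96/√(1−ρ)); stratified power = Φ(m − 1.96)

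Taking m = 2.80/√(1−ρ), which is 80% power when ρ = 0:

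| ρ | Size, plain | Power, plain | Power, stratified | Loss (points) |
|---|---|---|---|---|
| 0 | 5.0% | 80.0% | 80.0% | 0 |
| 0.02 | 4.8% | 80.2% | 80.8% | 0.5 |
| 0.04 | 4.6% | 80.5% | 81.6% | 1.1 |
| 0.10 | 3.9% | 81.3% | 84.0% | 2.7 |
| 0.20 | 2.8% | 82.7% | 88.0% | 5.3 |

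(Losses are computed before rounding.)

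**In shift terms.** A shift of 0.5 within-cell SD on each of two evenly split factors gives 2 × 0.5²/4 = 0.125, so ρ = 0.125/1.125 = 0.11. For normal changes and a 0.25 SD arm effect, m = 0.25 × √(400/4) × √(3/π) = 2.44. Power is Φ(2.44 − 1.96), about 68%, stratified, and Φ(2.44 − 1.96/0.943), about 64%, plain: a loss of about 4 points.

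**Simulation, same design, 0.25 SD arm effect:**

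| Change scores | Shift per factor | Plain | By site | By site × age |
|---|---|---|---|---|
| Normal | 0 | 69.2% | – | 69.0% |
| Normal | 0.25 SD | 68.9% | 69.2% | 69.0% |
| Normal | 0.5 SD | 65.1% | 67.5% | 69.1% |
| Exponential | 0 | 97.4% | – | 97.3% |
| Exponential | 0.5 SD | 88.2% | 92.5% | 97.5% |

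At 0.5 SD the losses are 69.1 − 65.1 = 4.0 points (normal) and 97.5 − 88.2 = 9.3 points (exponential). Site alone recovers 2.4 of 4.0 and 4.3 of 9.3. Sizes at 0.5 SD, in the same column order, were 4.3/4.7/5.3% (normal) and 2.9/3.4/4.8% (exponential). No setting inflated the plain test's size beyond simulation error, including scores rounded to 5 points or capped at the top.

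**Sensitivity to effect size.** The exponential case starts near 97% power, which compresses the loss. With the effect reduced so that power without shifts is about 78%, the exponential case gave 69.0% against 78.0% at 0.25 SD shifts and 53.7% against 77.8% at 0.5 SD. That is the most adverse combination examined.

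**The case against.** Several counter-arguments are sound.

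- **The effect is conditional.** Site or age must predict the change, not the level, and a change score already removes stable differences between cells. No document gives a figure. The nearest evidence is in Protocol 1.1, that grade 3 reactions to RZV become less frequent with age; SAP 8.3 takes the worst post-vaccination score, so a link is plausible. Nothing suggests that the sites differ.
- **The SAP's rule covers site only.** The primary and other reactogenicity tests are stratified by site alone, and age is handled by repeating the analyses within age groups. A reader might infer that the SAP breaks a promise to stratify by age; it made none. Age belongs here only because it was a randomization factor.
- **The larger loss needs strong skew.** With normal changes it is small.
- **Stratifying is not free in every case.** Van Elteren's test can lose power if arm effects point in different directions across strata, and the change departs from a test that the protocol names.
- **The objective is exploratory and unpowered.** That limits importance, not correctness.

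One argument does not carry. It could be said that the general clause in SAP 5.2 already turns the named test into its stratified form. But a specific unstratified test, set beside two analyses that each state their site adjustment, would most naturally be programmed as written.

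**Conclusion.** The inconsistency is real and minor. The named between-arm test omits the site stratification that SAP 5.2 calls for where applicable, and it ignores the blocking by site and age. With a 0.25 SD arm effect and shifts up to 0.5 SD per factor, the cost is 0 to about 4 points of power for normal changes and 0 to about 9 for strongly skewed ones. It is nil if neither factor predicts the change. Smaller effects combined with strong skew could cost more. All of these figures rest on assumed shifts, shape and effect.

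A reader might infer that the test is invalid or that false positives rise. The documents and calculations do not support that: the only direction is conservative. Nor do they support saying that the test is certainly conservative, or that the quality-of-life comparison is underpowered, because no prognostic effect and no target power are stated for it. The primary noninferiority analysis is site-stratified and untouched.

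**What to change.** In SAP 8.3, Exploratory Objective 8, replace the Mann-Whitney test with a van Elteren (stratified Wilcoxon) test. Stratify at least by site, as SAP 5.2 already commits, and preferably by the four site-by-age randomization cells. Within the age-group analyses, stratify by site only. If the plain test is kept on purpose, state why stratification does not apply.

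Record the change from the protocol-named test in the SAP version table. If the comparison has already been run, report the stratified test as a labelled sensitivity analysis.

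The cost is one sentence, one version-table entry and standard software. No sample size changes, and with four cells of this size the simulations showed no measurable power penalty when the cells do not matter.

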#### 7.1.4 Secondary and Exploratory Objectives

The statistical methodology described above for the Primary Objective will also be applied to all Secondary Objectives 1 and 2 and Exploratory Objectives 1, 2, 3, 5 and 6. For Secondary Objective 3 and Exploratory Objective 4, the proportion of participants with severe adverse events will be presented in a table along with exact 95% confidence intervals. The confidence intervals will be used to make comparisons and interpretations. For Exploratory Objective 7, seroconversion or seroprotection at day 29 will be compared using a Mantel-Haenszel statistic in a stratified analysis by site. HAI titer (GMTs) and the geometric mean fold rise (GMFR) in HAI titer will be compared using a regression model that will control for site or nonparametric testing if normality assumptions are not met.

For Exploratory Objective 8, the EQ-5D-5L responses are converted to a Utility Index that ranges from -0.109 (worst health) to 1.0 (best health) using the US specific value sets ([http://www.euroqol.org/fileadmin/user\\_upload/Documenten/Excel/Crosswalk\\_5L/EQ-5D-5L\\_Crosswalk\\_Value\\_Sets.xls](http://www.euroqol.org/fileadmin/user_upload/Documenten/Excel/Crosswalk_5L/EQ-5D-5L_Crosswalk_Value_Sets.xls)). The EQ VAS has a range of 0 (worst health) to 100 (best health). The changes from baseline will be assessed within vaccine group using a paired t-test for the index values and VAS. If normality assumptions are not met, the testing will be performed with a Wilcoxon signed-rank test. The Mann-Whitney U test (Wilcoxon rank-sum test) will be used to compare the difference scores from baseline between the two vaccine groups for the index values and VAS.

Proportions for all objectives will be presented in tables and the noninferiority comparisons will be presented in graphical displays as well. There will be no adjustment to the alpha level for these comparisons, with all noninferiority comparisons at the one-side alpha 0.025 level with a 10% noninferiority margin. The alpha level will be set at the two-side 0.05 level for Exploratory Objectives 7, 8, and 9.

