3.3 Exploratory

1. Proportion of participants with at least one severe (grade 3) solicited local or systemic reactogenicity event on days 1-8 after RZV dose 2 in each study group.
2. Proportion of participants with at least one severe (grade 3) solicited local reactogenicity event on days 1-8 after RZV dose 2 in each study group.
3. Proportion of participants with at least one severe (grade 3) solicited systemic reactogenicity event on days 1-8 after RZV dose 2 in each study group.
4. Proportion of participants with serious adverse events and adverse events of clinical interest after RZV dose 2 and clinical description of these events in each study group through the entire study period.
5. Proportion of participants with at least one moderate-to-severe (Grade 2-3) solicited local or systemic reactogenicity event on days 1-8 after RZV dose 1 in each study group.
6. Proportion of participants with at least one moderate-to-severe (Grade 2-3) solicited local or systemic reactogenicity event on days 1-8 after RZV dose 2 in each study group.
7. HAI titers by vaccination group and age group:
 - a. The proportion of subjects achieving seroconversion at day 29 (an HAI titer \geq 1:40 at day 29 if the baseline titer is $< 1:10$ or a minimum four-fold rise in HAI titer if the baseline titer is $\geq 1:10$) for each influenza strain in the respective season's vaccine.
 - b. Proportion of subjects with a seroprotective HAI titer ($\geq 1:40$) pre- and post-immunization at day 29 for each IIV antigen in the respective season's vaccine.
 - c. The geometric mean HAI titer (GMT) at baseline (Day 1) and Day 29 for each IIV antigen in the respective season's vaccine.
 - d. The geometric mean fold rise (GMFR) in HAI titer at Day 29 for each IIV antigen in the respective season's vaccine.
8. Change in scores on the EuroQOL 5 dimensions-5 level (EQ-5D-5L) and EuroQOL visual analogue scale (EQ VAS) pre-vaccination and post-vaccination will be compared between the vaccination groups and age groups.

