Fever (°C)	$\geq 37.5 - < 38.4^\circ \text{C}$ $\geq 100.0 - < 101.1^\circ \text{F}$	$\geq 38.4 - < 39^\circ \text{C}$ $\geq 101.1 - < 102.2^\circ \text{F}$	$\geq 39^\circ \text{C}$ $\geq 102.2^\circ \text{F}$

Table 1. Injection-site Reactogenicity

Fatigue/ Malaise	Fatigue that is easily tolerated	Fatigue that interferes with normal activity	Fatigue that prevents normal activity
Myalgia	Myalgia that is easily tolerated	Myalgia that interferes with normal activity	Myalgia that prevents normal activity
Arthralgia	Arthralgia that is easily tolerated	Arthralgia that interferes with normal activity	Arthralgia that prevents normal activity
Headache	Headache that is easily tolerated	Headache that interferes with normal activity	Headache that prevents normal activity
Gastrointestinal symptoms (nausea, vomiting, diarrhea, and/or abdominal pain)	Gastrointestinal symptoms that are easily tolerated	Gastrointestinal symptoms that interfere with normal activity	Gastrointestinal symptoms that prevent normal activity
Chills/Shivering	Shivering that is easily tolerated	Shivering that interferes with normal activity	Shivering that prevents normal activity

This information will also be presented by age-group for the subset of subjects aged 65-69 versus those subjects aged 70 years or older. No formal statistical hypothesis testing (i.e., no p-values) will be performed, only the confidence boundary of the difference will be presented.

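### Exploratory Objective 8 repeats its significance tests within each age group but plans no estimate of whether the arm difference varies with age

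*SAP*

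**What the plan says.** SAP 8.3, Exploratory Objective 8, sets out three kinds of analysis of change in the EQ-5D index and EQ VAS:

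- a linear regression of index change within vaccine group, adjusted for site;
- a site-stratified Mantel-Haenszel comparison of VAS change cut at 8 points;
- a rank test between arms: "The Mann-Whitney U test (Wilcoxon rank-sum test) will be used to compare the difference scores from baseline between the two vaccine groups", for both scores.

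It then adds: "The statistical tests described above will also be performed by age-group", the groups being 65-69 and 70 or older. On error control it says: "This testing will be considered exploratory with an alpha level of 0.05 with no alpha adjustment". Protocol 7.1.4 fixes sidedness: "The alpha level will be set at the two-side 0.05 level for Exploratory Objectives 7, 8, and 9". It gives no by-age method for this objective. SAP 5.2 has the general policy: "There will be no adjustments to the alpha level for multiple comparisons".

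The endpoint (SAP 3.3, item 8; same wording in Protocol 2.2.3) is that changes in the two scores "will be compared between the vaccination groups and age groups". The objective itself (SAP 2.3) asks for the arm comparison in the full population and by age group.

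For the primary objective, and likewise for Secondary Objectives 1-2 and Exploratory Objectives 1-3, 5 and 6, the SAP treats age groups differently: "No formal statistical hypothesis testing (i.e., no p-values) will be performed, only the confidence boundary of the difference will be presented". Exploratory Objective 7 is prepared by age with estimates and intervals. Exploratory Objective 8 is therefore the only objective for which the SAP plans significance tests inside each age group.

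**The concern.** Whether the vaccine effect on quality of life depends on age is a question about the difference between two arm differences. The plan produces a p-value for each age group and nothing that compares them. The Mann-Whitney comparison also comes with no planned effect estimate or interval, so for that comparison p-values are all a reader would have to set side by side.

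If one age group falls below 0.05 and the other does not, the natural summary is that quality of life is affected at one age only. That summary would have no direct support, because two strata with the same true effect can easily land on opposite sides of 0.05. At stake is how an exploratory finding by age is described in the report.

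**Working it through.** **The only power figure in the documents.** It belongs to the primary endpoint (SAP 4.3): 14% in both arms, margin 10 points, one-sided alpha 0.025, 80% power. Per arm, n = 2 × 0.14 × 0.86 × (1.960 + 0.842)² / 0.10² = 189.001, rounded up to 190, so 380 in total. With 5% drop-out, 380 / 0.95 = 400. Power at 190 per arm is 80.2%. The stated figures reproduce, but they say nothing about EQ-5D or EQ VAS.

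**Inputs for this point.** Two-sided alpha is 0.05 per test (Protocol 7.1.4), and the two age groups contain different people, so their tests are independent. The documents give no SD, effect size, power or age split for these scores; all of those are assumed below and shown as ranges. The normal approximation stands in for the rank test.

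**Split result with no effect.** P(exactly one significant) = 2 × 0.05 × 0.95 = 9.5% per test.

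**Split result with the same true effect in both groups.** Let d be the whole-trial noncentrality and f the share of participants in one age group.

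- Stratum power: a = Φ(d√f − 1.96) + Φ(−d√f − 1.96), and b likewise with 1 − f.
- P(exactly one significant) = a(1 − b) + b(1 − a).

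Example: 80% whole-trial power gives d = 1.96 + 0.84 = 2.80. With f = 0.5, d√f = 1.98, stratum power is 50.8%, and the split chance is 2 × 0.508 × 0.492 = 50%.

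| Whole-trial power | 50/50: stratum powers | 50/50: split | 30/70: stratum powers | 30/70: split |
|---|---|---|---|---|
| 20% | 12.4%, 12.4% | 22% | 9.4%, 15.4% | 22% |
| 50% | 28.3%, 28.3% | 41% | 18.9%, 37.5% | 42% |
| 80% | 50.8%, 50.8% | 50% | 33.5%, 65.0% | 55% |
| 90% | 63.0%, 63.0% | 47% | 42.7%, 77.4% | 54% |

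**On the VAS scale.** Take 190 per arm, a 50/50 split and assumed SDs of 15, 20 and 25. A common difference of 4 points gives a split result in 50%, 40% and 32% of trials. A common difference of 8 points gives 8%, 34% and 48%. The 8% arises because, at SD 15, each age group already has 95.7% power: 2 × 0.957 × 0.043 = 8%.

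**An interaction test instead.** When the effect is common, it declares an age difference 5% of the time whatever the size of the effect; a simulation of 400,000 draws gave 5.0%. In the same simulation (50/50 split), the interaction was significant in about 33% of split results with no effect, 12% at 50% power and 10% at 80% power.

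**Precision of the interaction.** Its standard error relative to the whole-trial effect is 1/√(f(1 − f)): 2.0 at 50/50 and 2.2 at 30/70.

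**The case against.** The case for leaving the plan alone has real substance. The objective is exploratory, the lack of alpha adjustment is stated openly, and the age groups are prespecified and used in randomization. The objective's wording asks for arm comparisons by age group, which separate analyses do deliver, and the endpoint wording could mean two separate comparisons. All of that stands and limits the weight of the point. It does not turn two p-values into evidence about a difference in effect, and no other by-age method is given.

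Four stronger readings are tempting, and the documents do not support them.

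- A reader might take 50% as the probability that an apparent age difference is chance. It is the probability of a split result given an identical true effect, equal age groups and 80% power. The reverse probability would need a prior on effect modification, which the documents do not give.
- A reader might infer that the SAP intends to conclude an age difference from discordant p-values. It nowhere says so.
- A reader might say that Exploratory Objective 8 breaks a SAP-wide ban on age-group p-values. The ban is written only for the reactogenicity objectives, and those have no interaction estimate either. This objective has its own explicit sentence, which may be a deliberate choice.
- A reader might count three tests in two age groups and quote 1 − 0.95⁶ = 26.5% for at least one false positive. That assumes independence, yet the VAS category is a cut of the same VAS change; with perfect correlation the figure is 1 − 0.95² = about 10%. It also reads the Mantel-Haenszel comparison as between arms, which the SAP does not state. And it concerns multiplicity, a disclosed policy, not effect modification.

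**Conclusion.** The point holds in limited form. The SAP plans significance tests within each age group and no estimate of how the arm difference varies between them, although the endpoint brings age groups into the comparison. If the true effect is common, a one-sided pattern of significance arises in 9.5% of trials per test with no effect. With an effect, it arises in about 22% to 55% across whole-trial power of 20% to 90% and age splits of 50/50 or 30/70. It is less frequent when the effect is very large relative to the SD (8% for 8 VAS points at SD 15). The corresponding rate for an interaction test is 5%. All but the no-effect and interaction figures depend on assumed power, SD, effect or age split. How often a split would be seen in this trial therefore cannot be stated from the documents. This is a cheap improvement; the primary conclusion does not depend on it.

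**What to change.** In SAP 8.3, Exploratory Objective 8:

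- For each of the EQ-5D index and EQ VAS, add a between-arm model of change on arm, age group, arm-by-age group and site. Use robust or bootstrap intervals: both scores are worst post-vaccination values on bounded scales, and the SAP asserts normality only for the index change.
- Report the arm-by-age contrast with its 95% CI.
- Replace the age-group p-values with the arm difference in each age group and its 95% CI, matching the presentation already used for the reactogenicity objectives.
- The Mann-Whitney test in the whole population can stay.

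The cost is SAP wording and one new exploratory model per score, with no new data. It is more than one added term, because the existing regression works within vaccine group and the arms are compared only by the rank test. The interaction estimate will be imprecise, with about twice the standard error of the overall effect at a 50/50 age split, and the report should say so.
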